6.3.2. Solicited Adverse Reactions

An AR is any AE for which there is a reasonable possibility that the test product caused the AE. The term "Solicited Adverse Reactions" refers to selected signs and symptoms occurring after injection administration during a specified post-injection follow-up period (day of injection and 6 subsequent days). The solicited ARs are recorded by the subject in eDiary. The occurrence and intensity of selected signs and symptoms is actively solicited from the participant during a specified post-injection follow-up period (day of injection and 6 subsequent days), using a pre-defined checklist (i.e., solicited ARs).

The following local ARs will be solicited by the eDiary: pain/tenderness at injection site, erythema (redness) at injection site, swelling/induration (hardness) at injection site, and groin or underarm swelling or tenderness ipsilateral to the side of injection.

The following systemic ARs will be solicited by the eDiary: fever, irritability/crying, sleepiness, and loss of appetite.

The AR categories are presented in Table 7 in the protocol.

The solicited ARs will be graded based on the grading scales presented in Table 7 in the protocol, modified from the Toxicity Grading Scale for Healthy Adult and Adolescent Volunteers Enrolled in Preventative Vaccine Clinical Trials (DHHS 2007). Investigator will assess Grade 4 events (with exception of fever).

If a solicited local or systemic AR continues beyond 7 days post injection, the participant's parent(s)/ LAR(s) should notify the site to provide an end date to close out the event on the reactogenicity page of the eCRF.

All solicited ARs (local and systemic) will be considered causally related to injection.

Analyses of solicited ARs will be provided by study part and treatment group for each injection (first or second) based on the associated subset of Solicited Safety Set, i.e. First (Second) Injection Solicited Safety Set, unless otherwise specified.

The number and percentage of subjects who reported each individual solicited local AR (has a toxicity grade of Grade 1 or greater) and solicited systemic AR (has a toxicity grade of Grade 1 or greater) during the 7-day follow-up period after each injection will be tabulated by vaccination group, toxicity grade, and injection (i.e., first or second injection). The number and percentage of subjects who reported each individual solicited AR will also

be summarized by vaccination group, toxicity grade, days of reporting and injection. In addition, a bar plot will be created to display the percentage of participants who reported each individual solicited AR after each injection.

A two-sided 95% exact confidence interval (CI) using the Clopper-Pearson method will be provided for the percentage of subjects who reported any solicited local AR, solicited systemic AR, or any solicited AR.

The onset of individual solicited AR is defined as the time point after each injection at which the respective solicited AR first occurred. The number and percentage of subjects with onset of individual solicited AR will be summarized by vaccination group, study day relative to the corresponding injection (Day 1 through Day 7), and injection.

The duration will be calculated as the end date/day of the solicited AR event – start date/day of the solicited AR event + 1, regardless of whether it is intermittent or continued. If the solicited AR continues beyond 7 days, the days a solicited AR is reported after 7 days will be included (e.g., an event that lasted 5 days in the first 7 days post injection and 3 days beyond 7 days post injection, the duration will be reported as 8 [5+3] days).

Characteristics of solicited ARs during the 7-day follow-up period after each injection will be provided, including descriptive statistics of day of onset and duration in days, as well as number and percentage of solicited ARs persisting beyond 7 days.

Solicited ARs collected on eDiary and those collected on reactogenicity aCRF will be provided in a listing, and the maximum grade from eDiary and aCRF will be presented. All solicited ARs that continue beyond 7 days post injection will be presented in separate data listings.

6.3.3. Physical Examinations and Vital Signs

Vital signs, including length/height, weight, and body temperature (via axillary route) will be presented in a listing.

Abnormal physical examination findings will be reported on the medical history or adverse events eCRF, as appropriate.

6.4. Immunogenicity Analysis

The analyses of immunogenicity will be based on the PPIS-Neg as the primary analysis population for both parts, unless otherwise specified. Participants from Part 1 and Part 2 in

the PPIS-Neg population who receive the same mRNA-1273.214 dose level selected for Part 2 may be combined for immunogenicity analyses.

The geometric mean concentration (GMC) and GM level will be calculated using the following formula:

$$10^{\left[\sum_{i=1}^{n}\log_{10}(t_{i})\right]}$$

where $t_1, t_2, ..., t_n$ are *n* observed immunogenicity concentrations or levels.

The geometric mean fold-rise (GMFR) measures the changes in immunogenicity concentrations or levels within subjects. The GMFR will be calculated using the following formula:

where, for *n* subjects, v_{ij} and v_{ik} are observed immunogenicity concentrations or levels for subject *i* at time points *j* and *k*, $j \neq k$, where *k* represent pre-injection baseline at Day 1.

6.4.1. Immunogenicity Assessments

Blood samples for immunogenicity assessments will be collected at the time points indicated in the Schedule of Assessments (SoAs) in Appendix E.

Immunogenicity assessments for both Part 1 and Part 2:

- Serum nAb concentration against SARS-CoV-2 as measured by pseudovirus and/or live virus neutralization assays, including VOC Omicron.
- Serum bAb level as measured by a multiplex ligand-binding assay specific to the SARS-CoV-2 S protein.
- Serum bAb level as measured by a multiplex ligand-binding assay specific to the SARS-CoV-2 nucleocapsid protein.
- Testing for serologic markers for SARS-CoV-2 infection as measured by anti-nucleocapsid antibodies detected by immunoassay.

6.4.2. Hypothesis Testing Strategy for Immunogenicity

The hypothesis tests for noninferiority, superiority, and "super" superiority of mRNA-1273.214 against Omicron as compared to mRNA-1273 primary series against Omicron will be performed sequentially. The noninferiority hypotheses (hypotheses HA¹ and HA²) will be tested first.

Once noninferiority is demonstrated based on both GMC or GM level and SRR, superiority (hypotheses $\rm HA^3$ and $\rm HA^4$) of mRNA-1273.214 as compared to mRNA-1273 primary series will be tested. If the lower bound of the 95% CI of the GMR is > 1, superiority based on GMC or GM level is demonstrated; if the lower bound of the 95% CI of the SRR difference is > 0%, superiority based on seroresponse is demonstrated.

Once superiority is demonstrated based on both GMC or GM level and SRR, "super" superiority (hypotheses HA⁵ and HA⁶) of mRNA-1273.214 as compared to mRNA-1273 primary series will be tested. If the lower bound of the 95% CI of the GMR is > 1.5, "super" superiority based on GMC or GM level is demonstrated; if the lower bound of the 95% CI of the SRR difference is > 10%, "super" superiority based on seroresponse is demonstrated.

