- 9) H_A^9 : The immune response of mRNA-1273.214 in participants 12 weeks to < 6 months is noninferior to the primary series of 100 µg mRNA-1273 in adults based on GMR against the SARS-CoV-2 original strain with a noninferiority margin of 1.5-fold (lower bound of CI for GMR > 0.67).
- 10) H_A^{10} : The immune response of mRNA-1273.214 in participants 12 weeks to < 6 months is noninferior to the primary series of 100 µg mRNA-1273 against the original strain in adults based on difference in SRR against the SARS-CoV-2 original strain with a noninferiority margin of < 5% (lower bound of CI for SRR > -5%).

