4.3. Sample Size and Power

In Part 2, approximately 600 infant participants 12 weeks to < 6 months of age will be enrolled at the dose level selected for Part 2, with an mRNA-1273.214 to placebo ratio of 1:1. Assuming 10% to 15% participants are not negative SARS-CoV-2 status at baseline, it is estimated that there will be a minimum of approximately 250 evaluable participants in the mRNA-1273.214 arm eligible for immunogenicity analyses.

The sample size of approximately 300 infant participants in the mRNA-1273.214 arm in Part 2 is considered to be sufficient to support a safety assessment. There is at least 90% probability to observe at least 1 participant with an AE at a true AE rate of 1% in this group.

The sample size calculation for each of the 2 primary noninferiority hypothesis tests (H_A^1 and H_A^2) was performed, and the larger sample size was chosen for the study.

• With approximately 250 evaluable participants receiving mRNA-1273.214 in the Per-Protocol Immunogenicity Subset - Negative (PPIS-Neg) in Study mRNA-1273-P206 and adults (≥ 18 years of age) in Study mRNA-1273-P301, there will be at least 90% power to demonstrate noninferiority of the immune response against Omicron variant, as measured by the geometric mean concentration (GMC) or GM level, in infant population at a 2-sided alpha of 0.05, compared with that in adults (≥ 18 years of age) in Study mRNA-1273-P301 receiving mRNA-1273, assuming an underlying geometric mean ratio (GMR) (which is calculated as ratio of GMC or

- GM level) value of 1 and the standard deviation of the natural log-transformed concentration/level is assumed to be 1.0, and a noninferiority margin of > 0.667.
- With approximately 250 evaluable participants receiving mRNA-1273.214 in the PPIS-Neg in Study mRNA-1273-P206 and adults (≥ 18 years of age) in Study mRNA-1273-P301, there will be at least 90% power to demonstrate noninferiority of the immune response against Omicron variant as measured by SRR in infants at a 2-sided alpha of 0.05, compared with SRR against Omicron variant in adults ≥ 18 years of age in Study mRNA-1273-P301 receiving mRNA-1273, assuming SRR of 60% to 70% in Study mRNA-1273-P301, true SRR improvement of 10% in infants from Study mRNA-1273-P206 compared with adults from Study mRNA-1273-P301, and a noninferiority margin of 5%.

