6.4.4. Secondary Analysis of Antibody-Mediated Immunogenicity Endpoints

The following secondary immunogenicity evaluations will be performed.

- For each group in Part 1, GM level of SARS-CoV-2-specific serum Ab with corresponding 95% CI will be provided at each time point. The 95% CIs will be calculated based on the t-distribution of the log-transformed values then back transformed to the original scale for presentation. The following descriptive statistics will be also provided at each time point at which blood samples are collected for immunogenicity: the number of subjects (n), median, minimum and maximum.
- For Part 2, the immune response as measured by the serum Ab GM value and SRR against SARS-CoV-2 VOC (Omicron) at 28 days after the second dose will be compared to the serum Ab GM value and SRR at Day 57 (at 28 days after the second dose) against original strain after mRNA-1273 primary series in Study P301 using the same analysis methods described in Section 6.4.3.
- For Part 2, the immune response as measured by the serum Ab GM value and SRR against SARS-CoV-2 original strain at 28 days after the second dose will be compared to the serum Ab GM value and SRR at Day 57 (at 28 days after the second dose) against original strain after mRNA-1273 primary series in Study P301 using the same analysis methods described in Section 6.4.3.

6.4.5. Exploratory Analysis of Antibody-Mediated Immunogenicity Endpoints The below exploratory analyses of immunogenicity for Part 1 and/or Part 2 may be performed if applicable.

- GM level of SARS-CoV-2-specific bAb with corresponding 95% CI will be provided at each time point. The 95% CIs will be calculated based on the t-distribution of the log-transformed values then back transformed to the original scale for presentation. The following descriptive statistics will be also provided at each time point: the number of subjects (n), median, minimum and maximum.
- GM fold-rise (GMFR) of SARS-CoV-2-specific bAb levels with corresponding 95% CI will be provided at each postbaseline timepoint over pre-injection baseline at Day 1. The 95% CIs will be calculated based on the t-distribution of the log-transformed values then back transformed to the original scale for presentation. The following descriptive statistics will be also provided at each time point: the number of subjects (n), median, minimum and maximum.

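### HA7 to HA10 are formal secondary hypotheses with no place in the testing sequence, and superiority is declared one endpoint at a time, so the secondary error rate is not held at one-sided 2.5%

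*SAP*

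**What the plan says.** SAP 4.2 and protocol 9.2 list HA3 to HA10 as secondary hypotheses, each with a numerical bound. HA7 and HA8 compare the infants' Omicron response with the adults' original-strain response. HA9 and HA10 compare original strain with original strain. They are worded as tests: HA10, for example, is noninferiority "in adults based on difference in SRR against the SARS-CoV-2 original strain with a noninferiority margin of" 5%.

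The strategy in SAP 6.4.2, repeated in protocol 9.5.1, covers mRNA-1273.214 against Omicron "as compared to mRNA-1273 primary series against Omicron will be performed sequentially". HA1 and HA2 must both be met before HA3 and HA4 are tested, and HA3 and HA4 must both be met before HA5 and HA6. Inside the last two steps, the geometric mean ratio (GMR) and the seroresponse rate (SRR) difference each have their own sentence declaring success on their own 95% bound.

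SAP 6.4.4 handles the HA7 to HA10 comparisons "using the same analysis methods described in Section 6.4.3". It adds no condition, order or alpha allocation. The conclusion table in SAP 6.4.3 assigns noninferiority, superiority and 'super' superiority separately for the GMR and for the SRR difference, without referring to the other endpoint.

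**The concern.** Four of the eight secondary hypotheses lie outside the sequence. Taken literally, the plan lets the report declare noninferiority on the original strain, or across strains, when the Omicron co-primary objective has failed. In the steps that are sequenced, two either-or claims each use the full one-sided 2.5%. The table in 6.4.3 goes further: a GMR lower bound above 1.5 earns 'super' superiority on GMR whatever the SRR result, which conflicts with the gates in 6.4.2. A reader who sees a sequential strategy will expect the secondary claims to carry its protection, and most of them do not.

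**Working it through.** **Inputs.** SAP 4.3 gives a "2-sided alpha of 0.05" (one-sided 0.025 for each lower bound), "approximately 250 evaluable participants" on the vaccine arm, an SD of the natural-log level of 1.0, true GMR 1, margin 0.667, adult SRR of 60% to 70%, infants 10 points higher, and an SRR margin of 5%. The adult number is not given; I assume 250, with 1000 as a sensitivity value. No correlations are given; I use a range. The gate calculations take adult SRR 65%.

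**The plan's own figure.** SAP 4.3 states "at least 90% power to demonstrate noninferiority".
- GMR: SE = √(1/250 + 1/250) = 0.0894; ln 1.5 = 0.4055; Φ(0.4055/0.0894 − 1.96) = 99.5%.
- SRR, 60% v 70%: SE = √(0.24/250 + 0.21/250) = 0.0424; Φ(0.15/0.0424 − 1.96) = 94.2%. For 70% v 80% it is 97.4%.

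The stated power holds with 250 adults. Neither document states an error rate for the secondary tests.

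**HA7 to HA10, all at their margins, ungated.** If independent, 1 − 0.975⁴ = 9.6%. Positive correlation lowers this (table below).

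**HA3/HA4 behind the HA1+HA2 gate, at GMR 1 and SRR difference 0.** HA2 passes with probability Φ(0.05/0.0427 − 1.96) ≈ 21.5%, where 0.0427 = √(2 × 0.65 × 0.35/250). HA1 passes with probability 99.5%. If independent:
- false HA3: 0.025 × 0.215 = 0.0054
- false HA4: 0.025 × 0.995 = 0.0249
- either: 0.0054 + 0.0249 − 0.0006 = 3.0%

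Simulation gives 3.7% at correlation 0.5 and 3.8% at 0.8 (at most 4.0% with 1000 adults). If the 6.4.3 table were followed and the gate ignored, the figure would be 3.9% to 4.5% at those correlations, and 1 − 0.975² = 4.9% if independent.

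**HA5/HA6, at GMR 1.5 and SRR difference 10 points:** 3.9% to 4.7%, by simulation.

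**Whole secondary family as written** (gates kept, HA7 to HA10 ungated at their margins, 250 adults). The overall range covers four Omicron settings (GMR, SRR difference): (1, 0), (1, 25 points), (2.5, 0) and (1.5, 10 points).

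| Correlation within pair / across pairs | HA7–HA10 alone | Overall |
|---|---|---|
| 0 / 0 | 9.6% | 11.9%–13.4% |
| 0.5 / 0.3 | 8.4% | 10.2%–11.7% |
| 0.7 / 0.5 | 7.2% | 8.7%–9.8% |
| 0.8 / 0.5 | 6.9% | 8.3%–9.3% |
| 0.9 / 0.8 | 5.3% | 6.0%–6.6% |

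Hand check of the top row at (1, 0): 1 − (1 − 0.0297)(1 − 0.0963) = 12.3%, against 12.4% simulated. The bound for six unprotected tests, ignoring gates, is 6 × 2.5% = 15%.

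**Joint null.** HA3 and HA7 share the infants' Omicron levels. Leaving aside the baseline adjustment, the HA7 ratio equals the HA3 ratio times (adult Omicron GM ÷ adult original-strain GM). Both are at their boundaries only if that adult ratio is 0.667. Likewise, HA4 at 0 and HA8 at −5% need the adult original-strain SRR to be 5 points above the adult Omicron SRR.

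**The case against.** The strongest reply is that silence is not permission. SAP 6.4.4 describes methods and does not say that HA7 to HA10 will be claimed after a primary failure. The sequence is expressly limited to Omicron versus Omicron, and neither document sets a familywise target for secondary hypotheses, so 2.5% is an outside benchmark. That is fair as a reading of intent. It does not remove the gap: hypotheses with success bounds and no gate leave the decision until after the data are seen, and nothing labels them unadjusted.

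Three stronger readings are tempting and are not supported.
- A reader might infer that the error rate is simply about three times 2.5%. Three independent tests would give 7.3%, but the documents fix neither that count nor any correlation, and the range is wide.
- A reader might put HA3/HA4 at about 5%. That ignores the HA1+HA2 gate, which holds it to 3% to 4%.
- A reader might infer that the primary conclusion is compromised. It is not: HA1 and HA2 must both succeed, and nothing later takes alpha from them.

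It is also fair that having every null at its margin is a worst case, given the adult ratio needed for HA3 and HA7 to be at their boundaries together.

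**Conclusion.** The concern stands for the secondary claims only. HA7 to HA10 are formal hypotheses without a gate. Superiority and 'super' superiority can each be claimed on one endpoint at full alpha, and the table in SAP 6.4.3 does not reflect the gates in 6.4.2. Secondary error is therefore not controlled at one-sided 2.5%. The worst case is roughly 5% to 10% for HA7 to HA10 alone, 3% to 4% for HA3/HA4 after the gate, and about 6% to 13% overall (6.0/2.5 = 2.4 to 13.4/2.5 = 5.4 times 2.5%).

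These sizes depend on the assumed correlations, 250 adults and adult SRR 65%; the documents give only the 60% to 70% range. The overall figure at GMR 1 and SRR difference 0 also needs HA3 and HA7 to be at their boundaries together. The calculation uses a single seroresponse definition. SAP 6.4.3 gives two without naming the one used for testing, which could raise the rate further.

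**What to change.** In SAP 6.4.2 and protocol 9.5.1:
- Keep the stated order HA1+HA2, then HA3+HA4, then HA5+HA6. Give HA9+HA10 and HA7+HA8 a prespecified place in the same fixed sequence, in an order the sponsor chooses before unblinding.
- Require both members of each pair at two-sided 0.05, stop at the first failure, and report later comparisons as nominal.
- Align the conclusion table in SAP 6.4.3 with these gates.

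This holds the total at 2.5% or less, because any false claim must pass the first step that contains a true null, and that null is rejected with probability at most 2.5%. Requiring both members within HA7/HA8 and within HA9/HA10 but leaving them ungated is not enough: with HA3/HA4 still either-or, the total is 3.1% to 5.1% at GMR 1 and SRR difference 0.

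Alternatively, label HA7 to HA10 descriptive with no noninferiority claim. HA3/HA4 and HA5/HA6 would still need both members for a claim.

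**Cost.** An SAP edit and a protocol 9.5.1 edit, possibly an amendment, since protocol section 9 requires one when methods for primary or key secondary hypotheses change before unblinding. The primary tests lose no alpha. The price is that later claims depend on earlier ones, so position matters: at the planning GMR of 1, the superiority step passes at most 2.5% of the time, and pairs placed behind it would rarely be formally tested. Pairs placed ahead of it stay reachable, but superiority then depends on them.

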6.4.3. Primary Analysis of Antibody-Mediated Immunogenicity Endpoints

For Part 2, the immune response as measured by the serum Ab GM value and SRR against SARS-CoV-2 VOC (Omicron) at 28 days after the second dose of mRNA-1273.214 will be compared to that of the young adult participants (18-25 years) at 28 days after the second dose of mRNA-1273 primary series in Study mRNA-1273-P301.

An analysis of covariance (ANCOVA) model will be carried out with the serum Ab value at 28 days after the second dose of IP (Day 85 for Study P206, Day 57 for Study P301) as the dependent variable and a group variable (mRNA-1273.214 vs. mRNA-1273) as the fixed variable, adjusted by the baseline serum Ab value. The serum Ab GM value at Day 85 for Study P206 and serum Ab GM value at Day 57 for Study P301 will be estimated by the geometric least square mean (GLSM) from the model. The GMR (Study P206 vs. Study P301) will be estimated by the ratio of GLSM. Its 2-sided 95% CI will also be provided to assess the difference in immune response between the Study P206 and Study P301 at 28 days after the second dose of IP.

The noninferiority of the GM value of mRNA-1273.214 compared with mRNA-1273 primary series will be demonstrated if the lower bound of the 95% CI of the GMR > 0.667.

In addition, the serum Ab GM value with its 95% CI and GMR with 95% CI will be provided at 28 days after the second dose of IP. The 95% CIs will be calculated based on the t-distribution of the log-transformed values then back transformed to the original scale. Descriptive summary statistics for serum Ab values including median, minimum, and maximum will also be provided.

The GMFR of serum Ab values with its 95% CI at 28 days after the second dose of IP over baseline (pre-Dose 1 of primary series) will be provided. Its 95% CIs will be calculated based on the t-distribution of the log-transformed values then back transformed to the original scale for presentation.

The number and percentage of participants with seroresponse due to vaccination will be provided with 2-sided 95% CI using Clopper-Pearson method at 28 days after the second dose of IP, where seroresponse at subject level is defined two ways:

- 1. as an Ab value change from baseline (pre-Dose 1 of primary series) below the LLOQ to $\geq 4 \times \text{LLOQ}$, or at least a 4-fold rise if baseline is $\geq \text{LLOQ}$.
- 2. as an Ab value change from baseline (pre-Dose 1 of primary series) below the LLOQ to \geq 4 × LLOQ, or at least a 4-fold rise if baseline is \geq LLOQ and <4 × LLOQ, or at least a 2-fold rise if baseline is \geq 4 × LLOQ.

The SRR difference with its 95% CI (using Miettinen-Nurminen score method) between pediatric participants receiving mRNA-1273.214 in Study P206 at Day 85 and adult participants receiving mRNA-1273 primary series in Study P301 at Day 57 will be provided.

The noninferiority of the SRR of mRNA-1273.214 compared with that of mRNA-1273 primary series will be demonstrated if the lower bound of the 95% CI of the SRR difference is > -5%.

The table below lists possible scenarios of GMR and SRR difference results and corresponding immunogenicity hypothesis testing conclusions.

Endpoints	Scenario		Conclusion
GMC or	1	Lower bound of 95% CI of GMR (GMC _{P206} /	Non-inferiority of mRNA-1273.214 in P206
GM level		GMC_{P301} or GM level _{P206} / GM level _{P301}) \leq	as compared to mRNA-1273 100 µg primary
Ratio		0.667	series (PS) in P301 based on GMR is not
			demonstrated

	3	$0.667 < Lower bound of 95\% CI of GMR$ $(GMC_{P206}/GMC_{P301} \text{ or } GM \text{ level}_{P206}/GM$ $level_{P301}) \leq 1$ $1 < Lower bound of 95\% CI of GMR$ $(GMC_{P206}/GMC_{P301} \text{ or } GM \text{ level}_{P206}/GM$	Non-inferior of mRNA-1273.214 in P206 as compared to mRNA-1273 100 µg PS in P301 based on GMR is demonstrated but superiority is not demonstrated. Superiority of mRNA-1273.214 in P206 as compared to mRNA-1273 100 µg PS in P301 based on GMR is demonstrated but "super"
	4	$ evel_{P301}) \le 1.5$ $Lower bound of 95\% CI of GMR$ $(GMC_{P206}/GMC_{P301} or GM evel_{P206}/GM $ $ evel_{P301}) > 1.5$	superiority is not demonstrated "Super" superiority of mRNA-1273.214 in P206 as compared to mRNA-1273 100 μg PS in P301based on GMR is demonstrated
SRR Difference	1	Lower bound of 95% CI of SRR difference $(SRR_{P206} - SRR_{P301}) \le -5 \%$	Non-inferiority of mRNA-1273.214 in P206 as compared to mRNA-1273 100 µg PS in P301 based on SRR difference is not demonstrated
	2	-5% < Lower bound of 95% CI of SRR difference (SRR _{P206} - SRR _{P301}) \leq 0	Non-inferiority of mRNA-1273.214 in P206 as compared to mRNA-1273 100 µg PS in P301 based on SRR difference is demonstrated but superiority is not demonstrated
	3	0 < Lower bound of 95% CI of SRR difference (SRR _{P206} - SRR _{P301}) $\leq 10\%$	Superiority of mRNA-1273.214 in P206 as compared to mRNA-1273 100 µg PS in P301 based on SRR difference is demonstrated but "super" superiority is not demonstrated
	4	Lower bound of 95% CI of SRR difference $(SRR_{P206} - SRR_{P301}) > 10\%$	"Super" superiority of mRNA-1273.214 in P206 as compared to mRNA-1273 100 µg PS in P301 based on SRR difference is demonstrated

